- 9. Is willing to provide fresh tumor tissue via tumor biopsy before the first dose of the study drug only if participant has a disease can be be safely accessed through a CT-guided/US-guided or percutaneous biopsy for multiple core biopsies judged by the investigator. If participant doesn't have a disease that can be safely accessed, they are still eligible.

Co-PI: [name] Date: 11/22/2022

- 10. Performance status (PS) of 0 to 2 on the Eastern Cooperative Oncology Group (ECOG) performance scale
- 11. Has adequate organ function as determined by the following laboratory values:
 - Absolute neutrophil count (ANC) $\geq 1,200 \text{ /mcL}$
 - Platelets $\geq 100,000 / \text{mcL}$
 - $Hgb \ge 9 g/dL$
 - Total bilirubin ≤ 1.5 x upper limit of normal (ULN) (up to ≤ 3 x ULN for patients with liver metastasis)
 - ALT and AST ≤ 2.5 x ULN (up to ≤ 5 x ULN for patients with liver metastasis)
 - Cockcroft-Gault GFR (mL/min/1.73 m²) \geq 50. Cockcroft-Gault GFR Creatinine Clearance Value = $[(140\text{-age}) \times \text{weight (kg)}]/(\text{Scr} \times 72) \times (0.85 \text{ for females})$.
- 12. Left ventricular ejection fraction (LVEF) \geq 50% by ECHO or MUGA scan.
- 13. Female patients must not be pregnant or breastfeeding and must be practicing a medically acceptable form of locally approved birth control, be sterile or post-menopausal. Male patients should be using a medically acceptable form of birth control during the trial or be sterile.
 - o Female patient: A female patient is eligible to participate if she is not pregnant, not breastfeeding, and at least one of the following conditions applies:
 - Not a woman of childbearing potential (WOCBP)

OR

- A WOCBP agrees to follow the contraceptive guidance during the treatment period and at least 6 months after the last dose of trial intervention and must refrain from breastfeeding for at least 2 months after the last grapiprant treatment.
- Additionally, WOCPB must have a negative urine pregnancy test no more than 7 days prior to starting treatment on-study.
- Male patients: A male patient must agree to use contraception during the treatment period and for at least 6 months after the last grapiprant treatment and refrain from donating sperm during this period.
- 14. Patient with known HIV including current or prior infection would be included if:
 - with CD4+ T-cell (CD4+) counts \geq 350 cells/uL
 - without a history of AIDS-defining opportunistic infections

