4.4.2 Dose Modification

For patients who do not tolerate the protocol-specified dosing schedule, adjustments in grapiprant and eribulin doses are permitted to allow the patient to continue the study treatment. All dose modifications must be based on the worst preceding toxicity as graded by the NCI-CTCAE version 5.0. Those will also be counted as DLT when it meets DLT definition. The DLT will be defined as any of the following be "probable," "possible," and "definite events occurring in the first 21 days (cycle 1):

- Any Grade 3 hematologic toxicity with the following changes: grade 3 platelet count (< 50,000/mm³–25,000/mm³) with associated bleeding (without bleeding, grade 4 platelet count [< 25,000/mm³] will be defined as DLT); grade 3 absolute neutrophil count (<1,000–500/mm³) that persists for 7 or more days despite of the use of the grown factor support or that is associated with fevers (febrile neutropenia). (Otherwise, grade 4 absolute neutrophil count [< 500/mm³] will be defined as DLT.)
- Hepatocellular injury is indicated by 3-fold or greater elevations above the ULN of ALT or AST in addition to the elevation of serum total bilirubin > 2 x baseline. In such cases, no other reason can be found to explain the combination of increased transaminases and total bilirubin such as viral hepatitis, preexisting or acute liver disease, or another drug capable of causing the observed injury (Hy's Law). For patients with liver metastasis, 6-fold or greater elevations above the baseline of ALT or AST in addition to the elevation of serum total bilirubin > 4 x baseline.
- All other grade 3+ electrolyte abnormality associated with clinical symptoms, regardless of duration.
- Grade 3 nausea or vomiting that does not improve to Grade 1 within 72 hours of initiating supportive therapy.
- Any other non-hematologic grade ≥ 3 toxicity deemed to be related to the study drug that lasts 72 hours or more will be considered a DLT.
- A grade \geq 3 laboratory abnormality that is determined to be of no clinical significance by the investigators will not necessarily constitute a DLT.
- Any death not clearly due to the underlying disease or extraneous causes.

Dose modification at the time of toxicities will be conducted as follows:

Product: Grapiprant
Protocol 2021-0077 Proprietary Information of MD Anderson
[name]
Product: Grapiprant

PI: [name] Co-PI: [name] Date: 11/22/2022

Grapiprant

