In the phase Ib part, we will set two dosing levels for grapiprant (300 mg and 200 mg). Grapiprant will start from 300mg BID daily and be initially tested in 3 patients. For the main study, we will set 2 dosing levels for grapiprant for dose reduction by the DLT in phase Ib part and 3 dosing levels for toxicity management in phase II part (**Table 1**). The major adverse events of grapiprant from previous clinical trials were not overlapped to those in eribulin; therefore, we will modify dosing based on the type of events. In the event of hepatic toxicity, we will modify the grapiprant first. The major reported adverse events for grapiprant from the phase I study include elevation of liver enzymes, colitis, myositis, and supraventricular tachycardia. The dosing modification for grapiprant will follow the instruction which is described later in this section. In case the patient had uncommon side effects, PI and clinical staff will discuss the event and determine which drug should be reduced dosing, the discussion of the event with the PI and the rationale (which drug to reduce) will be documented in the subject's chart. **Table 2** (grapiprant) and **Table 3** (eribulin) show the summary of dose modification and criteria for treatment interruption and re-initiation.

Table 2. Recommended grapiprant dose modifications and criteria for treatment interruption and re-initiation with treatment-related adverse events

DOSE MODIFICATIONS FOR GRAPIPRANT		
Toxicity (CTCAE 5.0 Grade)	Grapiprant Dose Modifications	
Non-Hematologic Adverse Events Not Otherwise Specified		
Grade 1	Administer symptomatic treatment as appropriate Continue study treatment at same dose	
	Follow-up:	

Product: Grapiprant
Protocol 2021-0077 Proprietary Information of MD Anderson
PI: [name]

Co-PI: [name] Date: 11/22/2022

	Symptoms resolve to baseline within 7 days:
	Provide close follow-up to evaluate for increased severity.
	Symptoms ongoing >7 days:
	Consider following algorithm for Grade 2 events.
Grade 2	Administer symptomatic treatment
	Investigate etiology
	Consider consulting subspecialist, biopsy, and/or diagnostic
	procedure
	Discuss with IKENA Oncology
	Follow-up:
	Symptoms ongoing >7 days or worsening
	• Consider interruption of study treatment
	• Resume study treatment at the same or lower dose if
	symptoms have improved to Grade 1
	* *
	• If potentially related to cumulative toxicity (past first cycle),

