Grade 1	Maintain dose level.
Grade 2	Omit dose until resolved to ≤ Grade 1, then restart at the same dose.
Grade > 3	Omit dose until resolved to ≤ Grade 1, then decrease 1 dose level.
HEPATIC	
AST or ALT	
Grade 1 (> ULN-3.0 x ULN)	Maintain dose level with liver function tests (LFTs)** monitored per protocol
Grade 2 (> 3.0– 5.0 x ULN) without	Omit dose until resolved to \(\le \text{Grade 1, then} \)
total bilirubin elevation to > 2.0 x ULN	-If resolved in ≤ 7 days, maintain dose level -If resolved in > 7 days, decrease 1 dose level
Grade 3 (> 5.0– 20.0 x ULN) without total bilirubin elevation to > 2.0 x ULN	Omit dose until resolved to ≤ Grade 1, then decrease 1 dose level
Grade 4 (> 20.0 x ULN) without bilirubin elevation to > 2.0 x ULN	Permanently discontinue patient from eribulin
AST and/or ALT and Albumin	

Product: Grapiprant

Protocol 2021-0077 Proprietary Information of MD Anderson

DI. [name]

PI: [name] Co-PI: [name] Date: 11/22/2022

AST and/or ALT > ULN-3.0 x ULN (grade 2) and albumin < LLN - 3 g/dL (grade 1)	Omit dose until resolved to ≤ Grade 1, then -If resolved in ≤ 7 days, maintain dose level -If resolved in > 7 days, decrease 1 dose level				
AST and/or ALT > 3.0–5.0 x ULN and albumin < 3 - 2 g/dL (grade 2) without total bilirubin elevation to > 2.0 x ULN	Permanently discontinue patient from eribulin				
Bilirubin (*for patients with Gilbert Syndrome these dose modifications apply to changes in direct bilirubin only)					
Grade 1 (> ULN-1.5 x ULN)	Maintain dose level with LFTs** monitored per protocol				
Grade 2 (> 1.5–3.0 x ULN) with ALT or AST \leq 3.0 x ULN	Omit dose until resolved to \leq Grade 1, then: If resolved in \leq 7 days, then maintain dose level If resolved in $>$ 7 days, then decrease 1 dose level				
Grade 3 (> 3.0– 10.0 x ULN) with	Permanently discontinue patient from eribulin				

Dose Modifications for eribulin

ALT or AST $\leq 3.0 \text{ x ULN}$

*Hepatic toxicity monitoring for patients with Gilbert Syndrome: total and direct bilirubin must be monitored, intensified monitoring applies to changes in direct bilirubin only; the monitoring includes the following LFTs: albumin, ALT, AST, total bilirubin, alkaline phosphatase.

LFTs include albumin, ALT, AST, total bilirubin, alkaline phosphatase, and GGT

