- Cycle 1 and 2: every other week (if visit schedule allows more frequent monitoring, this should be considered) or more frequently if clinically indicated, especially for patients with borderline acceptable AST/ ALT/ bilirubin* values
- Cycle 3 and onward: monthly or more frequently if clinically indicated

In case of any occurrence of ALT/AST/ bilirubin* increase \geq grade 2, LFTs must be monitored weekly or more frequently if clinically indicated until resolved to \leq grade 1.

In case of any occurrence of ALT/ AST/ bilirubin* increase \geq grade 3 LFTs must be monitored weekly or more frequently if clinically indicated until resolved to \leq grade 1; thereafter, the monitoring should be continued every other week or more frequently if clinically indicated. until the end of treatment with study medication

Patients who discontinued treatment with eribulin should be monitored weekly, including LFTs* or more frequently if clinically indicated until resolved to \leq grade 1 or stabilization (no CTCAE grade change over 4 weeks).

All other AEs	
Grade 1 or 2	Per physician discretion.
Grade 3	Omit dose until resolved to ≤ Grade 1, then decrease 1 dose level.
Grade 4	Permanently discontinue the patient from eribulin. Note: Omit dose for ≥ Grade 3 vomiting or Grade 3 nausea only if the vomiting or nausea cannot be controlled with optimal antiemetic treatment.

Protocol 2021-0077 Proprietary Information of MD Anderson PI: [name]

Co-PI: [name] Date: 11/22/2022

Dosing interruptions are permitted in the case of medical/surgical events or logistical reasons not related to study therapy (e.g., elective surgery, unrelated medical events, patient vacation, and/or holidays). Subjects should be placed back on study therapy within 3 weeks of the scheduled interruption. The reason for interruption should be documented in the patient's study record. Subjects who experience a recurrence of the same severe or life-threatening event at the same grade or greater with a re-challenge of grapiprant will be discontinued from trial treatment.

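### Table 3 labels AST/ALT above ULN to 3.0 x ULN as grade 2 in the low-albumin row but as grade 1 elsewhere; on the printed range, that row's eribulin restart rule cannot be applied

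*Combined protocol and SAP*

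**What the plan says.** Section 4.4.2 sets one grading scale for dose changes: "All dose modifications must be based on the worst preceding toxicity as graded by the NCI-CTCAE version 5.0". Table 3 then gives the eribulin rules for treatment-related events.

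In its AST/ALT block, the lowest category is "Grade 1 (> ULN-3.0 x ULN"), for which the dose is kept and liver tests are monitored. Grade 2 in that block is above 3.0 to 5.0 x ULN. There eribulin is withheld until grade 1 or lower, then resumed at the same dose if resolution took 7 days or less, or one level lower if it took longer.

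A separate block covers AST/ALT together with albumin. Its first row is triggered by "AST and/or ALT > ULN-3.0 x ULN (grade 2) and albumin < LLN - 3 g/dL (grade 1"), with the action "Omit dose until resolved to ≤ Grade 1, then -If resolved in ≤ 7 days, maintain dose level", followed by a one-level decrease if resolution took more than 7 days. Its second row, "AST and/or ALT > 3.0–5.0 x ULN and albumin < 3 - 2 g/dL (grade 2") without a bilirubin rise above 2.0 x ULN, requires permanent discontinuation of eribulin.

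**The concern.** The first combined row gives a grade 2 label to a range that the same table grades 1. This is more than a cosmetic slip, because the row's action depends on grade: the restart point and the later dose both hang on when the event has come down to grade 1 or lower. If the event starts there, the rule gives no usable instruction.

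At stake is the eribulin dose of a patient with mildly raised transaminases and mildly low albumin. One investigator might restart at once at full dose. Another might wait for values to normalise and then reduce. The eribulin text in section 4.4.2 rules out re-escalation after a toxicity reduction, so a reduction made under an unclear row would be permanent.

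**Working it through.** The plan states no figure for this point, so the check sets the rows side by side and tests the restart condition against the trigger.

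**Inputs (Table 3, section 4.4.2)**

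| Row | AST/ALT range | Albumin | Action for eribulin |
|---|---|---|---|
| AST/ALT, grade 1 | >1.0 to 3.0 x ULN | not part of the row | keep dose |
| AST/ALT, grade 2 | >3.0 to 5.0 x ULN | not part of the row | withhold to grade 1 or lower; 7-day dose rule |
| Combined, first row | >1.0 to 3.0 x ULN, labelled grade 2 | below LLN to 3 g/dL, labelled grade 1 | withhold to grade 1 or lower; 7-day dose rule |
| Combined, second row | >3.0 to 5.0 x ULN | below 3 to 2 g/dL, labelled grade 2 | discontinue permanently |

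**Step 1: is there a separate scale for the combined rows?** No. Section 4.4.2 applies CTCAE 5.0 to all dose modifications, the heading of Table 3 repeats it, and nothing defines a composite grade.

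**Step 2: suppose the printed range is right.** Any AST/ALT value that triggers the row lies above 1.0 and at or below 3.0 x ULN, which the table grades 1. The row itself grades the paired albumin 1. The worse of the two is max(1, 1) = 1, and the restart condition is grade ≤ 1. Every value that triggers the row therefore already satisfies the condition for leaving it. Time to resolution is 0 days for every patient, so the branch for more than 7 days can never be entered, and the branch for 7 days or less is met without any recovery. Deleting the label alone does not cure this.

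**Step 3: suppose the label is right.** The range should then read >3.0 to 5.0 x ULN. AST/ALT would start at grade 2, would have to fall to 3.0 x ULN or below, and the 7-day rule would work. But the action would then be the same as in the AST/ALT grade 2 row, so low albumin would add almost nothing and the row would be largely redundant.

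**Step 4: which element is the slip?** The evidence points both ways.
- For the range: low albumin appears to raise the action by one step. The lower range alone keeps the dose, and with low albumin withholds it. The higher range alone withholds, and with lower albumin discontinues.
- For the label: the action is identical to that of the AST/ALT grade 2 row, including the 7-day rule, which is what a grade 2 event would receive.

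**Step 5: does other text settle it?** No. The eribulin paragraph before Table 3 withholds the drug for grade 3/4 non-hematologic toxicity, and so supplies no restart rule here.

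**The case against.** The best defence is that this is a label error in one row with little practical reach, and much of that stands. Table 3 is headed as recommended. The row needs both abnormalities and a treatment-related event. For liver events, "In the event of hepatic toxicity, we will modify the grapiprant first". Section 4.12 leaves all dose decisions to the centre's investigators. Discretion limits the harm, but it does not tell the investigator when the hold ends. Text extraction is an unlikely explanation, since range and label share one cell and the restart problem remains without the label.

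Four stronger readings are tempting, and the documents do not support them.
- *The rule certainly fails.* It fails only if the printed range is the intended one (Step 3).
- *The table tells the investigator both to omit and to maintain eribulin.* Maintaining belongs to the row for AST/ALT alone. The combined row is more specific and says to withhold, and a stricter action with low albumin is not in itself an error. What is unclear is the restart.
- *Scheduled liver tests are too sparse for the 7-day rule.* That needs grade 1 monitoring and a running 7-day rule at the same time. At grade 1 the rule has nothing to time. At grade 2, "LFTs must be monitored weekly or more frequently if clinically indicated until resolved to" grade 1 or lower. Table 2 also has a 7-day check for grade 1 hepatic events, after which its grade 2 algorithm, with weekly liver chemistries, is to be considered.
- *Patients could trigger the row at entry.* Entry does allow "ALT and AST ≤ 2.5 x ULN (up to ≤ 5 x ULN for patients with liver metastasis"), and the listed laboratory criteria set no albumin limit. But Table 3 addresses treatment-related events, and section 5.3.1 records baseline toxicities as medical history, so an unchanged entry value should not trigger it. The entry limits matter only for how a new restart criterion is worded.

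**Conclusion.** The contradiction is real and can be seen within one table: the same AST/ALT range is grade 1 in one block and grade 2 in another. It follows, on the assumption that investigators act on the printed numeric range, that the hold has no working end point and the dose after it is undefined. If the label was intended, the restart rule is sound and the range is wrong. The row needs correcting either way, and the documents do not show which way.

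Confidence is high for the mismatch and low for the direction of the correction. The point is minor. It concerns one recommended row, the documents give no frequency for the combination, and no effect on dose can be quantified. Raised AST/ALT without low albumin, the DLT definition, the BOP2 boundaries and the sample size are unaffected.

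**What to change.** Ask the sponsor which element was intended, then correct the row in one of two ways.

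(a) If the range was intended, keep above ULN to 3.0 x ULN, relabel it grade 1, and replace the restart condition with one that is not already met at the trigger, such as AST/ALT and albumin back to baseline or normal. Baseline should be named, because a patient may enter with AST/ALT of up to 2.5 x ULN and might never reach normal.

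(b) If the label was intended, change the range to above 3.0 to 5.0 x ULN and keep the present restart rule, or delete the row as largely repeating the AST/ALT grade 2 row.

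The cost is one query and an edit to one table row at the next amendment. Nothing in the design or the analysis changes.

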Safety management guidelines, including dose modification algorithms, are provided. Please note, in cases where the investigator is directed to permanently discontinue study treatment, these instructions are mandatory as described in this section. An overview of the available grapiprant dose modification guidelines is presented in **Table 1**. All AEs are to be graded according to NCI-CTCAE, version 5.0 (http://ctep.cancer.gov). All dose modifications and the reason(s) for the dose modification must be documented in the eCRF. The major classes of grapiprant toxicity described in **Table 2** include "Cardiac", "Blood pressure", and "Gastrointestinal", "Renal", and "Hepatic".

Investigators should refer to the grapiprant IB and Eribulin PI for additional information regarding the background of each drug and the management of other AEs or potential safety-related issues.

In case a dose reduction is necessary, the dose level or schedule of grapiprant may be changed as determined by the investigator and IKENA Oncology, consistent with the instructions for dose level and schedule (**Table 2**). If either study treatment is deemed intolerable and requires discontinuation despite optimal management, as described below, the participant must be discontinued from the study treatment, unless clinical benefit has been demonstrated. Any participant who requires a decrease in the grapiprant dose below 100 mg BID will discontinue grapiprant treatment and will come off study. Patients may continue to receive eribulin off study per standard of care if clinical benefit has been demonstrated per attending physicican discretion. Any participant that is required to discontinue eribulin for an AE may only continue on grapiprant if clinical benefit has been demonstrated and with agreement from the IKENA Oncology.

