Persistent > Grade 2 regardless of etiology	Permanently discontinue patient from grapiprant	
RENAL		
Serum creatinine		
< 2 x ULN	Continue study treatment at same dose	
2–3 x ULN	Omit dose until resolved to ≤ Grade 1, then resume	
HEPATIC		
Grade 1	Administer symptomatic treatment as appropriate Continue study treatment at same dose Follow-up:	
	Symptoms and laboratory abnormalities resolve to baseline within 7 days: Provide close follow-up to evaluate for increased severity Symptoms or laboratory abnormalities ongoing > 7 days: Consider following algorithm for Grade 2 events	

Co-PI: [name] Date: 11/22/2022

Product: Grapiprant

Grade 2	Administer symptomatic treatment Monitor liver chemistries (ALT, AST, bilirubin) weekly until they resolve, stabilize or return to within baseline Investigate etiology Consider consulting subspecialist, biopsy, and/or diagnostic procedure Discuss with IKENA Oncology Follow-up: Symptoms or laboratory abnormalities ongoing >7 days or worsening: Consider interruption of study treatment
	 If interrupted, when symptoms and laboratory abnormalities have improved to Grade 1, resume study treatment at a lower dose of grapiprant (≤200 mg Q12h following the first dose reduction, and ≤100 mg Q12h following the second dose reduction) With a second dose reduction, change administration of grapiprant to 2 weeks on/ 1 week off
	If symptoms continue or worsen to Grade 3-4, follow algorithm for Grade 3-4 events
Grade 3	Interrupt or discontinue study treatment Consult subspecialist Monitor liver chemistries (ALT, AST, bilirubin) at least twice weekly until they return to Grade 2, then follow Grade 2 guidelines Discuss with IKENA Oncology
	Follow-up: Symptoms and laboratory abnormalities improve to Grade ≤1: • Resume study treatment at a lower dose of grapiprant (≤200 mg Q12h following the first dose reduction, and ≤100 mg Q12h following the second dose reduction) • With a second dose reduction, change administration of grapiprant to 2 weeks on/ 1 week off
	 Symptoms or laboratory abnormalities ongoing >7 days after Interruption: Discuss further management with consultant and IKENA Oncology Permanently discontinue study treatment
Grade 4	Permanently discontinue study treatment Monitor liver chemistries (ALT, AST, bilirubin) at least twice weekly until they return to Grade 2, then follow Grade 2 guidelines Immediately inform IKENA Oncology and MD Anderson
	Follow-up:

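### With albumin at 2-3 g/dL, Table 3 stops eribulin permanently at AST/ALT > 3-5 x ULN but allows a reduced-dose restart at > 5-20 x ULN

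*Combined protocol and SAP*

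**What the plan says.** All the rules are in section 4.4.2. Table 3 (eribulin) has a block for AST and/or ALT combined with albumin. Its second row opens "AST and/or ALT > 3.0–5.0 x ULN and albumin < 3 - 2 g/dL (grade 2") and carries a bilirubin condition, so that its second half reads "albumin < 3 - 2 g/dL (grade 2) without total bilirubin elevation to > 2.0 x ULN". The action is permanent discontinuation of eribulin. The block has no row for enzymes above 5 x ULN.

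The AST or ALT block above it sets no albumin condition:

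- "Grade 3 (> 5.0– 20.0 x ULN) without total bilirubin elevation to > 2.0 x ULN": hold until Grade 1 or less, then go down one dose level.
- "Grade 4 (> 20.0 x ULN) without bilirubin elevation to > 2.0 x ULN": permanent discontinuation.

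Three general statements bear on how the rows are read:

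- "All dose modifications must be based on the worst preceding toxicity as graded by the NCI-CTCAE version 5.0".
- For hepatic events, "In the event of hepatic toxicity, we will modify the grapiprant first".
- Under the Grapiprant heading, "in cases where the investigator is directed to permanently discontinue study treatment, these instructions are mandatory as described in this section".

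Table 2 (grapiprant), hepatic Grade 3, begins "Interrupt or discontinue study treatment Consult subspecialist". It allows resumption at a lower grapiprant dose after recovery to Grade 1 or less, and requires permanent discontinuation of study treatment if abnormalities last more than 7 days after interruption.

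**The concern.** A dose-modification table should not become more lenient as the toxicity worsens. At > 3-5 x ULN, albumin of 2-3 g/dL turns a temporary hold (the AST/ALT Grade 2 row) into a permanent stop. At > 5-20 x ULN the same albumin changes no written action. The protocol gives no reason why low albumin should be decisive at 4 x ULN and irrelevant at 10 x ULN. It looks like the effect of a closed upper limit on the combined row. A patient with the worse liver pattern could be re-exposed to eribulin under the written rule, while one with the milder pattern could not.

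The cell can be reached. Inclusion criterion 11 in section 4.2.1 admits patients with liver metastases at AST/ALT up to 5 x ULN and sets no albumin minimum. Section 6.2 reports Grade 2 or greater ALT elevation in 18% of eribulin patients with Grade 0 or 1 at baseline. Section 4.4.1 reports Grade 2/3 hepatic events in 18.5% and 14.3% of patients at grapiprant 300 mg BID. None of these figures gives the frequency of this exact pattern.

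**Working it through.** **Setting.** Albumin 2-3 g/dL, total bilirubin not above 2 x ULN, event treatment-related. Table 3's limits give five bands per enzyme. The actions are ranked: 0 = maintain or physician discretion, 1 = hold with the same dose possible, 2 = hold then reduce, 3 = permanent stop. Where several rows match, the strictest is taken. The stop row matches if either enzyme is in > 3-5 x ULN, because it says and/or.

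**Sequence by enzyme level, both enzymes in the same band.**

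| AST/ALT (x ULN) | Strictest matching rule in Table 3 | Rank now | Rank with proposed row |
|---|---|---|---|
| up to ULN | Grade 2 albumin alone: other AEs, discretion | 0 | 0 |
| > ULN-3 | AST/ALT Grade 1: maintain (the first combined row needs albumin of 3 g/dL or more) | 0 | 0 |
| > 3-5 | Combined row: permanent stop | 3 | 3 |
| > 5-20 | AST/ALT Grade 3: hold, then reduce | 2 | 3 |
| > 20 | AST/ALT Grade 4: permanent stop | 3 | 3 |

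**All AST x ALT pairs.** There are 5 x 5 = 25. By highest band they number 1, 3, 5, 7 and 9, the fourth being 4² − 3² = 7.

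- Peak > 3-5: all 5 stop.
- Peak > 5-20: in 2 the other enzyme is in > 3-5, so eribulin stops. In 7 − 2 = 5 it is not, so restart is allowed.
- Peak > 20: all 9 stop.

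Each of the 5 restart pairs is treated more leniently than a pair no worse on either enzyme. For example, moving the > 5-20 enzyme or enzymes down to > 3-5 turns restart into stop. So 5 of 25 pairs are inverted. With the proposed row, none is.

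**Which row governs on recovery.** A patient who peaked at > 5-20 x ULN must pass through > 3-5 on the way down. The worst-preceding-toxicity rule points to the Grade 3 row, and so to restart. If current values were used instead, the outcome would depend on whether a blood draw fell in the > 3-5 band while albumin was still low.

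**What Table 2 leaves open.** Assume that an abnormality is ongoing until it reaches Grade 1 or less, which Table 3 sets at 3 x ULN or less. Restart then needs this fall within 7 days:

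- from just above 5 x ULN: 1 − 3/5 = 40%
- from 10 x ULN: 1 − 3/10 = 70%
- from 20 x ULN: 1 − 3/20 = 85%

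A patient who achieves this is told to resume by Table 2 and to restart one level lower by Table 3, so both tables lead back to treatment.

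**The case against.** The strongest counter-argument is that the printed ranges, not the upper limit, are the slip. The first combined row carries a grade 2 label and the same action as the AST/ALT Grade 2 row, yet its range, > ULN-3 x ULN, is called Grade 1 elsewhere in Table 3. If both combined rows slipped down one band, the intended stop range would be > 5-20 x ULN, and the sequence at albumin 2-3 g/dL would be hold, stop, stop. This is possible but speculative. It would make the first combined row duplicate the AST/ALT Grade 2 action, whereas the printed ranges work as an escalation for low albumin. Under either reading > 5-20 x ULN with this albumin should be a stop, and the current text does not say so.

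Other safeguards make the gap rarer. Table 3 is headed as recommended, and a physician may stop eribulin anyway. Grapiprant is modified first. Table 2 requires a consult and liver chemistries at least twice weekly until Grade 2, so the > 3-5 band is likely to be seen during recovery. If grade 2 albumin itself counts as an ongoing abnormality, it too would have to recover within 7 days. A patient already at eribulin 0.7 mg/m² has no lower level to restart at. All of this stands as a limit on frequency. None of it changes the row, and discretion does not justify written advice that is milder for the worse enzyme level.

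It is also fair that 5 of 7 counts table cells, not patients, and that neighbouring gaps remain. At > ULN-3 x ULN, albumin from the lower limit of normal to 3 g/dL means hold, while albumin 2-3 g/dL means maintain or discretion. Patients with bilirubin above 2 x ULN also lie outside this point. The bilirubin rows are partly broken in the text available, so nothing is claimed about them; the rows used here are intact.

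**Conclusion.** The point holds. At albumin 2-3 g/dL and bilirubin not above 2 x ULN, Table 3 as written is stricter at > 3-5 x ULN than at > 5-20 x ULN. In 5 of the 7 band pairs that peak in the higher range, a reduced-dose restart is allowed. In practice the exposure is limited to patients whose enzymes return to 3 x ULN or less within 7 days of interruption. That limit assumes that Table 2's study treatment includes eribulin and that ongoing means not yet Grade 1 or less. The number of patients cannot be estimated from the documents and is probably small with 25 enrolled. The trial's operating characteristics are not at issue. This is a safety rule that is wrong as written and should be corrected.

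**What to change.** Reword the second combined row of Table 3 to: AST and/or ALT > 3.0 x ULN and albumin < 3 g/dL, without total bilirubin above 2.0 x ULN: permanently discontinue eribulin. This removes the upper enzyme limit and also the lower albumin limit; as printed, the row ceases to match below 2 g/dL. Add that where more than one row applies, the strictest governs. In the same amendment, reconcile the range and grade label of the first combined row, and confirm that > 3.0 x ULN is the intended lower limit of the stop row.

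The change is table wording only. Albumin, AST and ALT are already in the liver panel, so no tests are added. The bilirubin condition is unchanged, so patients above 2 x ULN are not affected. The downside is a few more permanent eribulin stops, including patients who would have recovered quickly.
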